6. RANDOMIZATION AND BLINDING

The study is a Phase 1/2 open-label, dose escalation and cohort expansion study and does not involve randomization; patients and members of the clinical study team will not be blinded to treatment.

7. SAMPLE SIZE AND POWER CALCULATION

This is a 2-part study: Part A (Dose-Escalation) and Part B (Cohort-Expansion).

Up to 30 patients were to have been enrolled in the 3+3 dose-escalation portion of the study (Part A).

The cohort-expansion portion of the study (Part B) will enroll up to 57 patients based on Simon's two-stage design. The first stage will recruit up to 9 patients in each of three cohorts. If at least 1 objective response is observed, a second stage recruitment will occur with up to 10 additional patients enrolled into that cohort, for a total of up to 19 patients per cohort. If at least 4 objective responses are observed in the 19 patients, then OBI-999 will be considered worthy of further evaluation in that indication. Patients will be followed up to the 24-week scheduled response assessment for the purposes of counting objective responses for Simon's two-stage design success criteria. This design is based on a level of low interest for a treatment with an ORR of 10% versus a level of high interest for a treatment with an ORR of 25%. The sample size is based on a one-sided alpha of 0.12 and 72% power. The two-stage design limits the number of patients treated for a treatment with low levels of activity.

8. ANALYSIS ENDPOINTS

Analysis endpoints are listed as per protocol. Only those endpoints marked with * will be analyzed in aCSR as per sponsor decision. Exploratory analyses are to be conducted by OBI Transnational Biology (or their designee) and may be included as appendices in the aCSR.

8.1 PRIMARY ENDPOINTS:

Part A (Dose-Escalation):

- AEs/ SAEs and laboratory abnormalities as graded by National Cancer Institute Common Terminology Criteria for Adverse Events (NCI CTCAE) version 5.0*.
- DLTs with OBI-999*.
- MTD and RP2D of OBI-999.

Part B (Cohort-Expansion):

- Percentage of patients with objective response*, clinical benefit, DOR and PFS according to Response Evaluation Criteria in Solid Tumors (RECIST) 1.1.
- Percentage of patients with ADAs in blood*.

8.2 SECONDARY ENDPOINTS:

Part A (Dose-Escalation):

- PK parameters of OBI-999 and its active metabolite MMAE*.

Part B (Cohort-Expansion):

- AEs/SAEs and laboratory abnormalities as graded by NCI CTCAE version 5.0*.
- PK parameters of OBI-999 and its active metabolite MMAE*.

8.3 EXPLORATORY ENDPOINTS:

Part A (Dose-Escalation):

- Potential predictive biomarkers for OBI-999 activity such as expression of Globo H and other tumor-associated glycans or tumor molecular phenotypes.

Part B (Cohort-Expansion):

- Potential predictive biomarkers for OBI-999 activity such as expression of Globo H and other tumor-associated glycans or tumor molecular phenotypes.

9. ANALYSIS POPULATIONS

Screen Failures Set: all patients who are considered screening failures. This analysis set will allow comparison of demographic and baseline characteristics for screen failures versus enrolled patients, to demonstrate that those who were excluded from the study were no different from those who had qualified and that there were no systemic biases in the enrollment of the study.

Screened Population: all patients who have signed informed consent.

Safety population: all enrolled patients who received at least 1 dose of study drug. This analysis set will be used for all safety endpoints.

Efficacy population: all enrolled patients who received at least one dose of study drug and had at least one follow-up tumor assessment scan. The efficacy population will be used as primary for analysis of clinical activity.

PK population: all enrolled patients who receive at least 1 dose of study drug and have sufficient PK samples (a sample at the end of administration and at least 3 samples during the elimination phase) to include in the PK assessments. This analysis set will be used for all PK endpoints.

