## 7.2 Treatment Discontinuation and Withdrawal of Patients

A patient who withdraws from the study within the DLT evaluation period for reasons other than drug related AE will be replaced.

A patient may voluntarily withdraw or be withdrawn from the study treatment at any time for reasons including, but not limited to, the following:

- Progressive disease.
- Grade 4 infusion reactions and OBI-999-related toxicity.
- Dose reductions required on more than 2 occasions for toxicity related to OBI-999.
- Treatment interruption for more than 2 consecutive doses for related or unrelated reasons.
- Patient withdrawal of consent: At any time, a patient's participation in the study may be terminated at his/her request or on the basis of the Investigator's clinical judgment.
- Inter-current illness: A condition, injury, or disease unrelated to the primary diagnosis that becomes apparent during treatment and necessitated the patient's termination from the study.
- General or specific changes in the patient's condition that renders him/her ineligible for further treatment according to the inclusion/exclusion criteria.
- Protocol deviation: The patient's findings or conduct fail to meet the protocol entry criteria or fail to adhere to the protocol requirements (e.g., drug noncompliance, failure to return for defined number of visits) such that the Sponsor and the Investigator agree that the deviation necessitates premature termination from the study.
- Lost to follow-up: The patient stops coming for visits, and study personnel are unable to contact the patient.

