### **15.7.2 Protocol Deviations**

Should a protocol deviation occur, the Sponsor must be informed as soon as possible. Protocol deviations and/or violations and the reasons for which they occurred will be included in the clinical study report. Reporting of protocol deviations to the IRB/IEC and in accordance with applicable Regulatory Authority requirements is an Investigator responsibility.

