10.4 PATIENT DISPOSITION

The number of patients screened and the reasons for screen failure from main consent, including

exclusion criteria met and inclusion criteria not met, will be tabulated overall in the screened population (all patients who have signed main informed consent) by Parts A and B.

Patients in each analysis population, as well as patients who complete the treatment, complete the study, and patients who prematurely discontinue from treatment and from the study, together with number of enrolled patients, will be tabulated as indicated in section 9.1. The number and percentage within each category will be presented by Parts A and B and by cohort (by dose level in Part A and by cancer type in Part B).

The number and percentage of patients included in the safety, efficacy and PK populations will also be conducted by study part and by cohort (by dose level in Part A and by cancer type in Part B).

A listing with all enrolled patients (all patients who have been screened and are eligible) will be generated for the study to describe country/study center, patient number, study part, cohort, date of Globo-H screening consent, Globo-H screening consent version, date of main informed consent, informed consent version, was informed consent withdrawn, date of withdrawal, first and last study drug dosing dates, total duration of study drug dosing, the reason for discontinuing study drug dosing, end of study (completion or discontinuation) date, and reason for discontinuing the study.

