10.7 ANALYSIS OF STUDY ENDPOINTS

This section describes analysis of primary, secondary and exploratory endpoints as per protocol. All endpoints will be analyzed using planned treatments. Summaries will be presented for safety population in Part A and Part B. Summaries for anti-OBI 999 antibodies (ADA) in Part B will be presented in PK and safety populations.

Only those analyses marked with * will be analyzed in aCSR as per sponsor decision.

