- In section §10.5, the protocol deviations will neither be summarized nor listed.
- In section §10.6.1, the baseline and demographic characteristics will be summarized using only the safety population and listed.
- In section §10.6.2, the medical history and current medical conditions will neither be summarized nor listed.
- In section §10.6.3, the prior and concomitant medications will neither be summarized nor listed.
- In section §10.6.4, the cancer history will be summarized using only the safety population and listed.
- In section §10.6.5, other medical history will not be listed.
- In section §10.6.6, prior cancer surgeries will neither be summarized nor listed.
- In section §10.6.7, prior cancer radiotherapy will neither be summarized nor listed.
- In section §10.6.8, prior cancer medication therapy will neither be summarized nor listed.
- In section §10.6.9, smoking history will neither be summarized nor listed.
- In section §10.7.1, adverse events that will be analyzed and listed have been marked with asterisks. Only ORR analysis using safety population and ADA analysis using safety and PK populations have been selected as CBR, DOR and PFS analyses will no longer be conducted for the aCSR. Only waterfall plot (bar plot) showing the best reduction in target lesion therapy will be presented for Cohort-Expansion patients.
- In section §10.8.1, only extent of exposure will be summarized, and all study drug administration data will be listed.
- In section §10.8.2, laboratory data will only be listed. OBI decided not to conduct normalization of local laboratory assessments; therefore, data will be listed as recorded.
- In section §10.8.3, vital signs data will only be listed.
- In section §10.8.4, electrocardiogram data will only be listed.
- In section §10.8.5, ECOG, physical examination and ophthalmological data will neither be summarized nor listed.

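### Part A safety is tabulated by planned rather than received dose, deviation outputs are dropped despite Protocol 15.7.2, and the word enrolled in the SAP 9 populations is ambiguous

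*SAP*

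**What the plan says.** **Treatment allocation in tables.** SAP 10.7, which introduces the primary, secondary and exploratory endpoints, states: "All endpoints will be analyzed using planned treatments". It places the summaries on the safety population. The Part A adverse event, laboratory and DLT outputs of SAP 10.7.1 fall under it, and SAP 10.1 presents Part A in columns for 0.4, 0.8, 1.2 and 1.6 mg/kg.

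**Deviations.** Protocol 15.7.2: "Protocol deviations and/or violations and the reasons for which they occurred will be included in the clinical study report". SAP 11, describing the abbreviated report: "In section §10.5, the protocol deviations will neither be summarized nor listed".

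**Populations.** SAP 9: "Safety population: all enrolled patients who received at least 1 dose of study drug". The efficacy and PK populations also start from enrolled patients. Protocol 14.2 uses the same construction, and neither section defines the word. The one gloss is a bracket in SAP 10.4: "A listing with all enrolled patients (all patients who have been screened and are eligible) will be generated for the study". SAP 9 also describes a "comparison of demographic and baseline characteristics for screen failures versus enrolled patients". Protocol 7.2 includes, among reasons for stopping treatment, patients whose findings or conduct "fail to meet the protocol entry criteria".

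**The concern.** Safety and tolerability is the first primary objective, and Part A describes safety by dose. In a study without randomisation (SAP 6) there is no randomised comparison for planned-treatment analysis to protect. Its only effect on a dose-level toxicity table is to credit an event to a dose that the patient did not receive.

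The deviation outputs are where an eligibility failure or dosing error would normally be summarised. SAP 11 removes them without mentioning the protocol's reporting commitment.

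The ambiguity over enrolled matters because the safety population carries both the adverse event tables and the only ORR kept for the abbreviated report (SAP 11). Two readings of that denominator are available in an open-label study, so the choice could be made with the results in view.

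**Working it through.** **1. The plan's own figures.** This point disputes no stated figure. The Simon design that sets the planned cohort sizes reproduces. The probability of success is the sum over x = 1 to 9 of C(9,x) p^x (1−p)^(9−x) × P[Bin(10,p) ≥ max(0, 4−x)].
- p = 0.25: 0.7201, against the stated 72% power.
- p = 0.10: 0.1100, below the stated 0.12.

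Nine per cohort at stage 1 is therefore a fair denominator for illustration.

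**2. Planned against received dose.** Part B has one dose level and is presented by cancer type, so planned and received dose cannot put a patient in different columns. The issue is confined to Part A. Take a planned column of n patients, one of whom received another level and is the only one with the event:
- by planned dose: 1/n
- by received dose: 0/(n−1)
- difference: 1/n

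The 3+3 rule gives levels of 3 to 6 patients: 1/3 = 33.3 points, 1/6 = 16.7 points. The column for the dose actually received errs the other way, showing 0/m where 1/(m+1) is right. These are hypothetical maxima, because no misdosed patient is documented.

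**3. Deviations.** What remains once the SAP 10.5 outputs are removed:
- PK Listing 3 (SAP Appendix III, section 3.3) covers deviations related to dosing or PK sampling. It could show a dosing error, but it is not designed to show eligibility failures.
- The listing of study drug administration data is kept (SAP 11).
- SAP 10.5 requires patients with major deviations to be identified before database lock. SAP 11 withdraws the outputs and does not mention this step.

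So the information is due to be assembled, but no planned output reports eligibility deviations.

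**4. Enrolled.** Two readings of the SAP 10.4 bracket:
- *Actually eligible.* A dosed patient later found ineligible is not enrolled and falls outside the safety population.
- *Passed screening.* The same patient was judged eligible, was enrolled, and stays in.

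For the second: SAP 10.5 planned to count patients with major deviations within the safety and efficacy populations, with no rule removing them. SAP 11 adds the safety population for efficacy because the scan requirement makes the efficacy population the more selective one. Nothing explicitly rules out the first.

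**5. Size if one patient is dropped.** From x/n:
- dropping a patient with the event gives (x−1)/(n−1), a fall of (n−x)/[n(n−1)]
- dropping one without it gives x/(n−1), a rise of x/[n(n−1)]

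Both are at most 1/n. For n = 9 that is 11.1 points. With one responder (Clopper-Pearson 95% intervals, as in the SAP):
- all nine kept: 1/9 = 11.1% (0.3 to 48.2)
- a non-responder dropped: 1/8 = 12.5% (0.3 to 52.7), a shift of 1.4 points
- the responder dropped: 0/8 = 0% (0 to 36.9), a shift of 11.1 points

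SAP 5.4 records two replacement patients in the pancreatic cohort. If 9 + 2 = 11 were treated there, the maximum is 1/11 = 9.1 points.

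**The case against.** A reader might infer something stronger: that a dosed patient later found ineligible drops out of every adverse event table and the ORR denominator, belongs to no analysis population, and leaves no trace. The documents do not support that.
- No section removes a dosed patient for ineligibility. The SAP 10.4 bracket describes a listing and can equally mean passed screening.
- Protocol 7.2 treats failed entry criteria as a deviation that may end participation, not as a reason to delete data. Adverse event collection (Protocol 12.5.1) runs from the first dose with no eligibility condition.
- Such a patient would still be in the Screened Population, which needs only signed consent.
- Not all deviation reporting is removed, since PK Listing 3 survives. The drug administration listing would also show that the patient was dosed.

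Those points stand, and they reduce the population issue to a wording ambiguity.

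On planned treatment, the objection is that no dosing error is documented. That is correct, but the rule as written still gives the wrong column if one occurred. The dose recommendation is not at risk: SAP 10.7.1 says that the RP2D was identified in Safety Review Committee review.

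On deviations, one can argue that SAP 11 discloses the removal, that Protocol 14 lets the SAP prevail over the protocol, and that the report's text could still describe deviations. Disclosure is real. But SAP 11 does not address Protocol 15.7.2, and a narrative without any output behind it cannot readily be checked.

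**Conclusion.** Two stated rules need changing and one term needs defining. SAP 10.7 assigns safety by planned dose, which would misplace toxicity after any Part A dosing error. SAP 11 drops deviation outputs without reconciling this with Protocol 15.7.2. The ambiguity over enrolled is the lesser matter: the SAP's other provisions suggest that dosed patients are kept whatever their later eligibility, but it never says so.

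The size is conditional. The documents do not show that any misdosed or dosed-but-ineligible patient exists; with none, every estimate is unchanged. The figures in the working assume exactly one such patient, in a cohort of nine or a dose level of three to six. No go/no-go decision is affected either, because SAP 5.4 records that the formal stage 1 analysis never took place.

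**What to change.** - **SAP 10.7:** summarise safety endpoints, including DLTs, by the dose level actually received at Cycle 1 Day 1. DLTs are confined to the first cycle, so this matches their observation period.
- **SAP 11 and 10.5:** provide a listing of major protocol deviations with reasons. SAP 10.5 itself planned a summary of major deviations and a listing only of COVID-19-related ones, so the text should say that the listing covers all major deviations, including eligibility failures.
- **SAP 9:** define the safety population as all patients who received at least one dose of OBI-999, regardless of eligibility, and define enrolled once, in the same section.

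The cost is a few sentences and one listing drawn from deviations that SAP 10.5 already requires to be identified before database lock. If no patient is affected, the tables stay as they are.

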### **14.2 Analysis of Populations**

The safety population to be analyzed will include all enrolled patients who receive at least 1 dose of study drug. The population used for analysis of clinical activity will be all enrolled patients who received at least one dose of study drug and had at least one follow-up tumor assessment scan.

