10.3 HANDLING OF MISSING DATA

Partial or missing start and end dates of AEs and concomitant medications will be imputed conservatively based on the rule described in Appendix II: Imputation rules for missing dates. The imputed dates will be used to allocate the AEs and concomitant medications to a study period, and to determine whether an AE is/is not treatment emergent. Listings of the AEs and concomitant medications will present the actual partial dates; imputed dates will not be shown in the listings.

For ORR endpoint, patients with missing data (for any reason) will be included as non-responders in the statistical analysis for each related follow-up analysis. For analyses performed in the safety population, patients who discontinue due to toxicity or clinical progression prior to post-baseline tumor assessments will be considered as non-responders and retained in the denominator.

For CBR endpoint, patients with missing data (for any reason) will be included as non-responders in the statistical analysis for each related follow-up analysis.

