CR	PD	SD provided minimum criteria for SD duration met, otherwise PD
CR	NE for all subsequent time points	SD provided minimum criteria for SD duration met, otherwise NE
PR	CR	PR
PR	PR	PR
PR	SD	SD
PR	PD	SD provided minimum criteria for SD duration met, otherwise PD
PR	NE for all subsequent time points	SD provided minimum criteria for SD duration met, otherwise NE
NE	NE	NE

[1] If a CR is truly met at first timepoint, then any disease seen at a subsequent timepoint, even disease meeting PR criteria relative to baseline, makes the disease PD at that point (since disease must have re-appeared after CR). Best response would depend on whether minimum duration of SD was met. However, sometimes 'CR' may be claimed when subsequent scans suggest small lesions were likely still present and in fact the patient had PR, not CR at the first timepoint. Under these circumstances, the original CR should be changed to a PR and the best response is PR.

Objective Response Rate (ORR) is defined as the percentage of patients with confirmed PR or CR based on tumor assessment as determined by RECIST 1.1 among all the patients in the safety and efficacy populations. A confirmed response will be defined as two or more consecutive assessments separated by at least 3 weeks. For summaries in the safety population, patients who discontinue due to toxicity or clinical progression prior to post-baseline tumor assessments will be considered as non-responders and retained in the denominator. A summary with the number of patients by BOR categories, ORR and the Clopper-Pearson 95% confidence interval (CI) for the ORR will be provided.

A by-patient swim lane plot of time (weeks) to Overall Response will be provided, along with waterfall plots (bar plot) showing the best reduction in target lesion therapy will be presented for Cohort-Expansion patients.

Sample code for ORR is provided below:

```
proc freq data=data;
by cohort;
tables AVAL/binomial alpha=0.05 nocum norow;
exact binomial;
run;
```

If the BOR used for ORR based on unconfirmed and confirmed overall responses differs by 10%, then we will present the same summary for ORR based on unconfirmed overall responses as a sensitivity analysis.

B. Clinical Benefit Rate

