11. DEVIATIONS FROM ANALYSIS AS DESCRIBED IN THE PROTOCOL

In the section §14.2 of the protocol the safety population is defined as all enrolled patients who receive at least 1 dose of study drug. The population used for analysis of clinical activity is defined as all enrolled patients who received at least one dose of study drug and had at least one follow-up tumor assessment scan, but it was not clearly stated this is the efficacy population. We clearly defined it in section §8 of the SAP.

The DOR is defined in section 14.3 of the protocol as the time from date of confirmed PR or CR to date of progression, but as we are applying a censoring rule to patients who are alive at the time of the analysis, we updated the definition in section 9.7.1 of the SAP to time from date of confirmed PR or CR to date of progression or death (from any cause).

OBI-999 2.0 mg/kg was planned to be administered in Part A but this dose was not administered to any subjects in Part A due to the toxicity observed with the 1.6 mg/kg dose. For this reason, this cohort will not be presented.

Efficacy endpoints will be analyzed in the safety and efficacy populations, because the definition of the efficacy population specifies that patients must have at least one follow-up assessment scan and so is closer to a per protocol population.

DLTs will not be derived and will be presented as collected on the eCRF. The following DLTs have been updated:

- “≥ Grade 3 fatigue, nausea and vomiting or diarrhea that does not resolve to Grade 1 or Baseline within 72 hours despite optimal supportive care” has been revised to “≥ Grade 3 fatigue, nausea and vomiting or diarrhea for more than 72 hours despite optimal supportive care”.
- “Any other Grade 3 or Grade 4 non-hematological toxicity (except Grade 3 fatigue, nausea, vomiting, or diarrhea lasting < 24 hours with optimal therapy, Grade 3 non-hematologic laboratory abnormalities that resolve to Grade 1 or baseline within 14 days)” has been

revised to. Any \geq Grade 3 non-hematological toxicity (except Grade 3 fatigue, nausea, vomiting, or diarrhea lasting < 24 hours with optimal therapy, Grade 3 non-hematologic laboratory abnormalities that resolve to Grade 1 or baseline within 14 days)".

On 10 November 2023, Sponsor stated they stop the OBI-999-001 study and elected to generate an aCSR. Therefore, as per sponsor decision, the planned analyses have been changed to:

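### Does the SAP's efficacy-population label, or its silence on replaced stage 1 patients, put the reported ORR in doubt?

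*SAP*

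**What the plan says.** Protocol 14.2 bases clinical activity on enrolled patients who "received at least one dose of study drug and had at least one follow-up tumor assessment scan". SAP 9 calls this the efficacy population and gives it primary status: "The efficacy population will be used as primary for analysis of clinical activity". The safety population in SAP 9 is all enrolled patients with at least one dose.

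On missing data, SAP 10.3 says that for ORR "patients with missing data (for any reason) will be included as non-responders in the statistical analysis". For the safety population it adds that "patients who discontinue due to toxicity or clinical progression prior to post-baseline tumor assessments will be considered as non-responders" and stay in the denominator. Protocol 14.3 contains the same retention rule.

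SAP 10.7.1 defines ORR "among all the patients in the safety and efficacy populations" and says that "ORR and the Clopper-Pearson 95% confidence interval (CI) for the ORR will be provided". SAP 10.7 says that endpoint summaries are presented for the safety population in both parts. SAP 11 explains that both sets are used because the efficacy population is "closer to a per protocol population". It then narrows the abbreviated report: "Only ORR analysis using safety population and ADA analysis using safety and PK populations have been selected".

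SAP 5.4 records that four stage 1 patients had no post-baseline RECIST assessment and that it was decided to replace them. Two pancreatic replacements were enrolled and two colorectal replacements were being sought when the sponsor stopped the study on 10 November 2023. The formal go/no-go analysis did not take place.

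**The concern.** Read alone, SAP 9 makes an evaluable-only ORR the primary result. Section 11 does not produce that analysis, and the ORR it does produce carries no primary label. A reader relying on SAP 9 could expect the four unscanned patients to be left out. Dropping patients who were never scanned is a familiar way for a single-arm response rate to drift upwards, because early toxicity and early clinical progression are common reasons for having no scan.

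The replacement decision adds to the doubt. The protocol's only replacement rule covers withdrawal during the DLT period, which belongs to Part A. Part B has no rule for replacing unscanned patients, and SAP 5.4 does not say whether replaced patients stay in the denominator or whether replacements add to the nine. Had a go/no-go followed, the counting rule could have changed the operating characteristics of the Simon design.

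**Working it through.** **1. The planned design.** Inputs from SAP 7: at least 1 response in 9, then at least 4 in 19; ORR 10% versus 25%; one-sided alpha 0.12; power 72%.

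P(success) = sum over x1 = 1 to 9 of Bin(x1; 9, p) × P(X2 ≥ 4 − x1), with X2 ~ Bin(10, p).

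- p = 0.25: 0.720, matching the stated power.
- p = 0.10: 0.110, within the stated alpha of 0.12.

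**2. Which ORR is reported.**

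| Place | Population for ORR |
|---|---|
| Protocol 14.2 | Scanned patients |
| Protocol 14.3 | Unscanned patients who stop for toxicity or clinical progression stay in as non-responders |
| SAP 9 | Efficacy population named primary |
| SAP 10.7 | Safety population |
| SAP 10.7.1 | Both |
| SAP 11, abbreviated report | Safety population only |

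The tension starts inside the protocol, between 14.2 and 14.3. Version 2.0 of the SAP leaves the planned text standing and narrows it with asterisks and section 11. Sections 10.5 and 10.6.3, for example, still describe outputs that section 11 cancels. SAP 9 fits that pattern, so an analyst following section 11 produces one ORR, in the safety population.

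**3. How replaced and replacement patients count in that ORR.** The safety population takes in every dosed patient, whether replaced or a replacement. The any-reason rule in SAP 10.3 makes each one without data a non-responder. SAP 10.1 uses non-missing observations as the denominator only where nothing else is specified, and here something else is specified. The denominator is therefore determined without a further line in SAP 5.4.

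**4. Direction.** An unscanned patient cannot have a confirmed response, so the number of responders is the same in both sets and only the denominator differs. The safety-population ORR is always equal to or below the efficacy-population ORR.

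**5. Size.** Stage 1 is capped at 3 × 9 = 27, so four unscanned patients are at least 4/27 = 14.8% of it. The documents give no response counts. The rows below assume nine patients dosed before replacement in each affected cohort, two unscanned in each (inferred from the two replacements per cohort), and both pancreatic replacements dosed and scanned. Clopper-Pearson 95% limits are the 0.025 quantile of Beta(x, n − x + 1) and the 0.975 quantile of Beta(x + 1, n − x). For x = 0 the upper limit is 1 − 0.025^(1/n).

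| Cohort | Responses | Safety population | Efficacy population |
|---|---|---|---|
| Colorectal | 1 | 1/9 = 11.1% (0.3–48.2) | 1/7 = 14.3% (0.4–57.9) |
| Colorectal | 0 | 0/9, upper limit 33.6% | 0/7, upper limit 41.0% |
| Pancreatic | 1 | 1/11 = 9.1% (0.2–41.3) | 1/9 = 11.1% (0.3–48.2) |
| Pancreatic | 0 | 0/11, upper limit 28.5% | 0/9, upper limit 33.6% |

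The point estimate moves by 14.3 − 11.1 = 3.2 points in colorectal and 11.1 − 9.1 = 2.0 in pancreatic. The zero-response upper limit moves by 41.0 − 33.6 = 7.4 and 33.6 − 28.5 = 5.1 points.

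**6. What the counting rule would have done to a go/no-go.** At a true ORR of 10%, the chance of passing stage 1 is 1 − 0.9^9 = 61.3% with nine patients and 1 − 0.9^11 = 68.6% with eleven. Two extra patients give at least one response with probability 1 − 0.9² = 0.19. With eleven in stage 1 and ten in stage 2, full-design success at 10% rises from 11.0% to 14.8%. None of this was realised, because no decision was taken.

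**The case for a change.** The best case for a change is that the text is inconsistent and the repair is cheap. The SAP governs where it differs from the protocol (Protocol 14), so its primary label matters, and section 11 lists many changes without listing that one. The specific safety-population sentence in SAP 10.3 names only toxicity and clinical progression, while SAP 5.4 does not say why the four patients were unscanned. The pancreatic ORR pools replacements with the patients enrolled before them, so it does not by itself show the count among the nine for which stage 1 was designed.

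The first part stands as an editorial observation: SAP 9 and SAP 11 do not agree on a label. The second does not create a gap, because the preceding sentence of SAP 10.3 covers missing ORR data from any cause. That sentence also has work to do in the efficacy set, for example when a later or confirmatory scan is missing, so it does not contradict SAP 9. The third is true but of little use now. A separate count for the patients enrolled before replacement would be post hoc and would inform a decision that was abandoned. Anyone who wants it should be able to reconstruct it from the tumor response listing (SAP 10.7.1) and the enrolled-patient listing with consent and dosing dates (SAP 10.4, which section 11 does not cancel). The table shells are in a separate document, so the exact layout of those listings could not be checked.

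**Conclusion.** No change to the plan is needed. The unreconciled label in SAP 9 is a clerical leftover from narrowing the analysis to an abbreviated report. The silence in SAP 5.4 is a gap that the population definition and the missing-data rule already fill. Following the SAP as written gives one ORR per cohort, with all dosed patients in the denominator and missing data as non-response, which is the more conservative of the two analyses and has direct support in Protocol 14.3.

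Under the assumptions in the illustration, the choice of set is worth about 2 to 3 percentage points on a one-response ORR and about 5 to 7 points on a zero-response upper limit. With no responses the point estimate is 0% in either set. Rewording SAP 9 would alter none of these reported figures. The conclusion rests on the go/no-go not having been run, as SAP 5.4 states, and on the report following section 11. Had the Simon decision gone ahead, the counting rule for replacements would have needed to be settled first.
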